8.4.1.2. Secondary Endpoints

The secondary endpoints will be analyzed as described below.

Change from Baseline endpoints

Change in TCD flow velocity from Baseline to Week 48 and Week 96 will be analyzed with the same MMRM as described for the primary endpoint (change from Baseline in TCD flow velocity at Week 24). A single model will be fit incorporating data from all timepoints.

Change in Hb and clinical measures of hemolysis (unconjugated bilirubin, % reticulocytes, absolute reticulocyte, and LDH) from Baseline at Week 24, Week 48, and Week 96 will be analyzed with a similar approach.

TCD responder endpoint

The TCD responder endpoint, defined as a TCD flow velocity reduction from Baseline ≥ 15 cm/sec at a given timepoint, eg, Week 24, Week 48, or Week 96, will be analyzed using an exact Cochran-Mantel-Haenszel (CMH) general association test stratified by the randomization stratification factors for the treatment difference between voxelotor and placebo.

A sensitivity analysis will be performed to assess TCD response definition with various TCD cutoff values in addition to the proposed 15 cm/sec.

Time to event endpoints

For time to conversion from conditional to abnormal TCD, the Kaplan-Meier method will be used to estimate the landmark rates and the associated 95% confidence intervals in the voxelotor and placebo groups at Week 24, Week 48, and Week 96. A log-rank test stratified for the randomization stratification factors will be used to test the difference between voxelotor and placebo groups. A Cox proportional hazard model may be used to estimate the hazard ratio, as appropriate.

Time to conversion to abnormal will be calculated as the number of weeks from the date of randomization to the date of TCD assessment when a TCD flow velocity \geq 200 cm/sec is first observed. For participants who withdraw from the study without conversion to abnormal or who reached analysis data cutoff date without TCD flow velocity reaching abnormal range, their time to conversion to abnormal will be censored at the date of last TCD assessment prior to study withdraw or analysis data cutoff date, as applicable.

Time to reversion from conditional to normal TCD will be analyzed using a similar approach.

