6. GENERAL STATISTICAL CONSIDERATIONS

6.1. Sample Size and Power

The sample size is planned to provide sufficient statistical power for the primary efficacy analysis and for a robust safety database. In addition, the number of events required to assess the secondary efficacy endpoint of time to conversion to abnormal TCD category is also considered.

For the primary endpoint (change from Baseline in TCD flow velocity [cm/sec]), assuming equal allocation across treatment groups and a common variance, an estimate of the number of subjects in each of 2 treatment groups used the following assumptions in the power calculation:

- Targeted treatment effect: difference in mean change from Baseline in TCD flow velocity is 15 cm/sec
- Common standard deviation is 24 cm/sec
- A significance level of 5% (2 -sided)

Assuming a 20% drop out rate, a sample size of 112 subjects per group provides > 95% power to detect the targeted treatment effect for the following hypothesis test using a Student's t-test:

$$H_0: \mu_1 = \mu_2 \quad \text{vs.} \quad H_A: \mu_1 \neq \mu_2,$$

where μ_1 and μ_2 stand for mean change from Baseline in TCD flow velocity at Week 24 in voxelotor and placebo groups, respectively.

For the secondary efficacy endpoint of time to conversion to abnormal TCD category, assuming 35% of subjects in the placebo group have experienced a TCD flow velocity > 200 cm/sec by Week 96, a hazard ratio of 0.5 between voxelotor group and placebo, a fixed follow up time of up to 96 weeks for each subject, and an overall 20% drop out rate, a total of 49 events is expected. This provides approximately 65% power for a log-rank test at a two-sided significance level of 5% (PASS version 11).

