Confirmed abnormal TCD event: TCD \geq 200 cm/sec but < 220 cm/sec for first assessment and \geq 200 cm/sec for repeat TCD assessment	Date of first TCD value \geq 200 cm/sec but < 220 cm/sec	Event
Abnormal TCD not requiring confirmation: TCD value \geq 220 cm/sec	Date of TCD assessment \geq 220 cm/sec	Event
No abnormal TCD event observed: All TCD < 200 cm/sec as of data cutoff date TCD \geq 200 cm/sec but < 220 cm/sec for first assessment and < 200 cm/sec for repeat TCD assessment	Date of last TCD assessment with a non-missing value prior to data cutoff date	Censored
Confounding event prior to abnormal TCD: Initiation of postbaseline HU without having experienced an abnormal TCD (either confirmed abnormal TCD event or abnormal TCD event not requiring confirmation) Withdraw from study without having experienced an abnormal TCD (either confirmed abnormal TCD event or abnormal TCD event not requiring confirmation)	Date of last TCD assessment with a non-missing value prior to start of HU or study termination date	Censored
Missing two or more consecutive TCD assessments immediately prior to an observed abnormal TCD: TCD \geq 220 cm/sec immediately after two or more consecutively missed TCD assessments TCD \geq 200 cm/sec but < 220 cm/sec for first assessment and \geq 200 cm/sec for repeat TCD assessment immediately after two or more consecutively missed TCD assessments	Date of last TCD assessment with a non-missing value prior to the two or more consecutively missed TCD assessments	Censored

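### SAP Table 2 censors a child at a gap of missed TCDs only when the next TCD is abnormal, so the rule removes only observed conversions and biases the exploratory conversion rates downward

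*SAP*

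**What the plan says.** Table 2 in SAP 8.2.2.2 sets event and censoring dates for time to conversion. Its last row covers this situation: "Missing two or more consecutive TCD assessments immediately prior to an observed abnormal TCD". The abnormal result must be 220 cm/sec or more, or 200 to below 220 and confirmed on repeat. Such a child is censored, and the date assigned is "Date of last TCD assessment with a non-missing value prior to the two or more consecutively missed TCD assessments".

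A child who never has an abnormal TCD falls under a different row, described as "All TCD < 200 cm/sec as of data cutoff date", with the date "Date of last TCD assessment with a non-missing value prior to data cutoff date". That row has no condition about gaps, and neither does the row for withdrawal or HU initiation.

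Protocol 8.4.1.2 has no missed-visit rule. It dates conversion at the assessment when a velocity of at least 200 "cm/sec is first observed. For participants who withdraw from the study without conversion to abnormal". The SAP change summary shows that the gap row came in with version 2.0. SAP 6.4.2.2 covers only withdrawal and data cutoff, and refers to Table 2.

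Under SAP 6.3 and 8.2.6, time-to-event endpoints are now exploratory: estimates and 95% CIs are presented without formal testing. SAP 8.2.2.2 still specifies landmark rates at Weeks 24, 48 and 96 and a hazard ratio. SAP 8.2.8 lists sensitivity analyses for change in TCD only.

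**The concern.** Kaplan-Meier and Cox estimates require that, at any time, censored children have the same prospects as those who stay at risk. Here the result after the gap decides whether a child is censored. If it is abnormal, the conversion is deleted and follow-up is cut back to before the gap. If it is below 200, the gap counts as event-free time at risk. Information from beyond the gap is kept when favourable and discarded when unfavourable.

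A gap makes the date of conversion uncertain. It casts no doubt on whether conversion occurred. The rule treats uncertainty about when as if it were uncertainty about whether.

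At stake are the conversion rates and the hazard ratio. Conversion is the category change that the protocol links to high stroke risk (Section 1.1) and to stopping study drug (Section 3.1.1). No planned analysis would show how much the row changes these estimates.

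**Working it through.** **Inputs from SAP 6.1.** 112 children per arm, 20% dropout, 96 weeks of follow-up, and an assumed voxelotor-to-placebo hazard ratio of 0.5. The control-arm assumption reads "35% of subjects in the placebo group have experienced a TCD flow velocity > 200 cm/sec by Week 96".

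**The plan's own figures.** Voxelotor risk at Week 96 is 1 − 0.65^0.5 = 0.194. Expected events are 112 × (0.350 + 0.194) × 0.80 = 48.7, or 49 as stated. Power in the Freedman form is Φ(√49 × (1 − 0.5)/(1 + 0.5) − 1.96) = Φ(0.373) = 64.6%, matching the stated 65%. These figures are not in dispute.

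**The same gap, two results.** Two children each have a TCD at Week 24, miss Weeks 36 and 48, and attend Week 60.

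| Week 60 TCD | Table 2 coding | Time at risk |
|---|---|---|
| 225 cm/sec | Censored at Week 24 | Ends at Week 24 |
| 190 cm/sec | Followed to last TCD or a later conversion | Includes Weeks 24 to 60 |

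Only the first record is altered, and it is a conversion.

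**Share of conversions removed, by hand.** Assume TCDs every 12 weeks (eight visits), each missed independently with probability m. For a conversion well inside follow-up, the chance that the first abnormal TCD comes straight after two or more misses is 1 − (1 − m)² − 2m(1 − m)². At m = 0.10 this is 1 − 0.810 − 0.162 = 2.8%. Near baseline and near Week 96 there is less room for a gap. Over the eight intervals the probabilities are 0.010, 0.019, 0.028, 0.028, 0.028, 0.027, 0.018 and 0.009, which sum to 0.167. Detected conversions sum to 7.889. With equal weight per interval, the share is 0.167/7.889 = 2.1%.

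**Simulation.** 200,000 children per arm, exponential conversion times, 20% dropout, and misses unrelated to TCD. The symmetric rule censors every child at the last TCD before a gap of two or more, whatever the next result. Entries are Week 96 conversion, placebo/voxelotor, in percent; the true values are 35.0/19.4.

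| Visits missed, both arms | Conversions removed | Protocol (no gap rule) | SAP Table 2 | Symmetric rule |
|---|---|---|---|---|
| 5% | 0.5% | 35.0/19.5 | 34.8/19.4 | 35.0/19.5 |
| 10% | 2% | 35.0/19.4 | 34.4/19.1 | 34.9/19.4 |
| 20% | 8% | 35.5/19.7 | 33.4/18.3 | 35.5/19.7 |
| 30% | 16% | 35.8/19.8 | 31.1/16.9 | 35.7/19.8 |

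Against no rule, the placebo rate falls by 35.0 − 34.4 = 0.6 points at 10% missed and by 35.8 − 31.1 = 4.7 points at 30%. The voxelotor falls are 0.3 and 2.9 points. The no-rule coding itself drifts up slightly at high missingness; against the true 35.0%, the fall at 30% is 3.9 points. The symmetric rule stays close to no rule throughout, so the asymmetry causes the fall.

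With equal missingness the hazard ratio is 0.50 to 0.51 under all three codings. With unequal missingness it moves under Table 2 only:

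| Missed, placebo/voxelotor | No rule | SAP Table 2 |
|---|---|---|
| 10%/20% | 0.51 | 0.48 |
| 10%/30% | 0.51 | 0.44 |
| 30%/10% | 0.51 | 0.59 |
| 10%/30%, true ratio 1 | 0.99 | 0.87 |

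**Other schedule.** The TCD rows of Appendix B are not legible in the text available, and SAP 8.2.2.3 uses TCDs at both Week 24 and Week 28, so a strict 12-weekly schedule is a simplification. With a TCD at every listed visit from Week 4, about 2%, 8% and 18% of conversions are removed at 10%, 20% and 30% missed. The placebo rate falls from 35.2% to 34.6% at 10% and from 35.6% to 30.4% at 30%.

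**The case against.** The strongest objection concerns weight. Time to conversion has left the test sequence and will be reported as an exploratory estimate from partial data. At 10% missed visits, 2% of 49 events is about one child, and early termination makes 49 unlikely to be reached. With about 31 and 17 events, the standard error of the log hazard ratio is √(1/31 + 1/17) = 0.30, so a ratio of 0.5 has a 95% CI of about 0.28 to 0.90. The shift from 0.51 to 0.44 is 0.15 on the log scale, half a standard error. Protocol 6.18 asks for missed assessments to be rescheduled, and the SAP Table 1 windows are contiguous, so long gaps may be few. All of this stands, and it keeps the point minor. It does not make the rule sound.

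The row is also prespecified, and the Week 48 analysis, with time-to-event summaries, has been performed. Silently replacing the coding now would be a post-hoc change. That stands too, and it shapes the fix.

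A reader might infer more than the documents support:

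- **That the rule favours voxelotor.** No direction follows unless missed visits differ by arm, and the documents give no rate for either arm.
- **That gaps cluster before conversion, so the loss is large.** Nothing in the documents indicates this.
- **That any two earlier misses trigger the row.** They must be consecutive and directly precede the abnormal TCD.
- **That the primary analysis contradicts Table 2 by treating the same child as a converter.** The imputation in SAP 6.4.2.1 and 8.2.1 fills missing velocities after an abnormal TCD for children discontinued from the study for conversion. It is a missing-data rule for a different estimand and does not classify events.

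**Conclusion.** The point holds as a minor one. The last row of Table 2 makes censoring depend on the outcome and can remove only observed conversions, so Kaplan-Meier conversion rates are biased downward in both arms. This follows from the text alone.

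The size rests on assumptions: the TCD schedule, the missed-visit rate, independence of misses from TCD, and the SAP 6.1 planning rates with full 96-week follow-up. On that basis the Week 96 bias is under 1 point at 10% missed visits or fewer, and reaches about 4.7 points (placebo) and 2.9 points (voxelotor) at 30%. The hazard ratio is essentially unaffected when missingness is equal. When it is unequal, the ratio moves in favour of the arm with more missed visits. The primary result and the formal test sequence are untouched.

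**What to change.** - Add an analysis that counts the conversion at the first observed abnormal TCD, as in protocol 8.4.1.2, or treats it as interval-censored between the last TCD before the gap and that date.
- Present it beside the current Table 2 coding, for both the landmark rates and the hazard ratio.
- State by arm how many children the row reclassifies. If there are none or very few in each arm, that count largely settles the matter.
- Label the addition as made after the Week 48 analysis.

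The cost is one more coding of an existing endpoint and a count. With the protocol's date, the event for a few children is late by up to the length of the gap; interval censoring avoids this at the price of a slightly less familiar method.

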8.2.2.3. TCD Response Endpoint

The TCD responder endpoint, defined as a TCD flow velocity reduction from Baseline \geq 15 cm/sec at Week 24, Week 48, or Week 96, will be analyzed using an exact Cochran-Mantel-Haenszel (CMH) general association test stratified by the randomization stratification factors for the treatment difference between voxelotor and placebo. The difference in percent

090177e1a2bf4d41\Approved\Approved On: 31-Jan-2025 17:16 (GMT)

responders between treatment groups with corresponding 95% CI using the Mantel-Haenszel stratum weight method will be presented. The analysis will be performed separately for each timepoint of interest. Missing data will be handled per Section 6.4.2.3, with subjects with a missing value at the assessment timepoint classified as non-responders.

For the analysis of TCD response at Week 24, the average of TCD values at Week 24 and Week 28 will be used as a sensitivity analysis. If the TCD assessment is missed at one time point, the TCD value at the other (non-missing) time point will be used. Subjects with missing TCD values at both Week 24 and Week 28 timepoints will be classified as non-responders.

In addition, a sensitivity analysis will be performed to assess an alternative TCD response definition based on a TCD flow velocity reduction from Baseline ≥ 30 cm/sec. Analyses will be performed separately for the Week 24, Week 48, and Week 96 time points.

8.2.3. Change from Baseline in Hemoglobin and Measures of Hemolysis

Change in hemoglobin and percent change in clinical measures of hemolysis (unconjugated bilirubin, % reticulocytes, absolute reticulocyte, and LDH) from Baseline at Week 24, Week 48, and Week 96 will be analyzed with a similar MMRM as described for the primary efficacy endpoint, change from Baseline in TCD flow velocity, with the exception that the baseline lab value will be included as a covariate. For each parameter, a single model will be fit incorporating available data from all timepoints, including to Week 96. Missing data will be handled per Section 6.4.2.4.

Figures displaying the relationship between change from baseline in TCD flow velocity and change from baseline in Hb at Weeks 24, 48, and 96 will be generated.

In addition, the percentage of subjects with a Hb response (defined as > 1 g/dL increase from Baseline) at Week 24 will be calculated by treatment arm for all randomized subjects (ITT population). The Study Visit Hb value for Week 24 will be the average of Hb values at Week 24 and Week 28. If the Hb assessment is missed at one time point, the Hb value at the non-missing time point will be used. Subjects with missing Hb assessment at both Week 24 and Week 28, initiation of HU post randomization and prior to Week 24, or a transfusion within 8 weeks of the Week 24 Hb assessment will be considered a Hb non-responder.

[figure not shown]

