5.7.3. Transfusion

Participants who require chronic transfusion will be discontinued from study treatment and 28 days later undergo the EOS visit. Transfusion for surgery or trauma is permitted.

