6.4.2.4. Hemoglobin and Hemolysis Change from Baseline

- For the primary method of analysis of these endpoints (MMRM), missing at random (MAR) will be assumed.
 - For change from baseline in Hb, a sensitivity analysis using last observation carried forward (LOCF) for subjects that discontinue the study early due to conversion to abnormal TCD flow velocity will also be performed.
- Subjects initiating HU postbaseline are to be discontinued from the study. Assessments of Hb and clinical measures of hemolysis obtained after HU initiation will be excluded from analysis.
- RBC transfusions: all laboratory results within 8 weeks after the transfusion date will be imputed for the MMRM change from baseline analysis of Hb and hemolysis measures. Post transfusion results will be imputed by data from the most recent Study

090177e1a2bf4d41Approved\Approved On: 31-Jan-2025 17:16 (GMT)

Visit prior to the transfusion (including Baseline) with a non-missing laboratory value.

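### Hb response is judged on the Week 24 and Week 28 values together, but its transfusion rule counts 8 weeks from the Week 24 draw only and gives no direction

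*SAP*

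**What the plan says.** SAP 8.2.3 adds a responder summary to the Hb analysis: "the percentage of subjects with a Hb response (defined as > 1 g/dL increase from Baseline) at Week 24 will be calculated by treatment arm". The value classified is not a single draw: "The Study Visit Hb value for Week 24 will be the average of Hb values at Week 24 and Week 28". If one draw is absent, the other stands alone: "If the Hb assessment is missed at one time point, the Hb value at the non-missing time point will be used".

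Three situations make a child a non-responder: no Hb at either visit, starting HU before Week 24, and the transfusion clause, "or a transfusion within 8 weeks of the Week 24 Hb assessment will be considered a Hb non-responder".

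The other transfusion rule for Hb is in SAP 6.4.2.4. It covers a different analysis and states its direction: "all laboratory results within 8 weeks after the transfusion date will be imputed for the MMRM change from baseline analysis of Hb and hemolysis measures". Transfusion can occur in children who stay on study. Protocol 5.7.3 takes children who need chronic transfusion off study treatment but adds: "Transfusion for surgery or trauma is permitted".

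**The concern.** Two draws can decide the classification, but the transfusion clause looks at one of them. The 6.4.2.4 rule does not fill the gap, because it is written for the MMRM only. Where the SAP wants such a rule for a responder endpoint it says so, as in 6.4.2.3 for TCD response. For Hb response, the clause in 8.2.3 is therefore the only protection.

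Transfusion raises Hb directly, so the clause has to separate a rise on study drug from a rise due to donor blood. Without a stated direction, and without mention of Week 28, two programmers could follow the text and produce different percentages. One could leave a transfused Week 28 value in the average. The other could mark a child as a non-responder for a transfusion that came too late to affect either value.

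**Working it through.** The documents state no rate, power or sample size for Hb response, so there is no figure to reproduce. The check is a day count, followed by a scale calculation on stated assumptions.

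**Inputs**
- Week 24: target Day 168, protocol range 161–175, analysis window 141–182. Week 28: target Day 196, protocol range 189–203, analysis window 183–224 (SAP 6.4.1, Table 1).
- 8 weeks = 56 days. Following 6.4.2.4, a draw on day d counts as affected by a transfusion on days d − 56 to d.
- Planned size: 112 per arm (SAP 6.1).

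**Step 1. Days that matter, at target visits.** Week 24 is affected by Days 112–168 and Week 28 by Days 140–196. At least one value is affected on Days 112–196, which is 85 days.

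**Step 2. Look-back reading.** The clause captures Days 112–168. It misses Days 169–196 (28 days), all within 8 weeks before the Week 28 draw. Hypothetical child: change +0.2 at Week 24 and +2.5 after transfusion at Week 28. The average is (0.2 + 2.5)/2 = 1.35 g/dL, a responder.

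**Step 3. Either-side reading.** The clause captures Days 112–224 and misses none of the 85 days. It also captures Days 197–224 (28 days), after both draws. Hypothetical child: changes +1.4 and +1.3, average 1.35 g/dL, but a transfusion on Day 210 makes the child a non-responder.

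**Step 4. Other visit timings.** Let g be the days between the draws. Look-back misses min(g, 57) days. Either-side misses max(0, g − 56) days and captures max(0, 56 − g) days after both draws.

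| Draw days | g | Look-back: missed | Either-side: missed | Either-side: after both draws |
|---|---|---|---|---|
| 168, 196 (target) | 28 | 28 | 0 | 28 |
| 175, 189 (protocol, closest) | 14 | 14 | 0 | 42 |
| 161, 203 (protocol, furthest) | 42 | 42 | 0 | 14 |
| 182, 183 (analysis, closest) | 1 | 1 | 0 | 55 |
| 141, 224 (analysis, furthest) | 83 | 57 | 27 | 0 |

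In the last row look-back misses 57 days, not 83. Days 142–167 fall after the Week 24 draw and more than 56 days before the Week 28 draw (224 − 56 = 168), so they affect neither value.

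**Step 5. Week 24 missing.** Week 28 alone is classified, and the clause has no draw to count from under either reading.

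**Step 6. Scale, by assumption.** With r transfusions per child-year, P(at least one in 28 days) = 1 − exp(−r × 28/365.25).
- r = 0.1: 0.76%, or 0.0076 × 112 = 0.9 children per arm.
- r = 0.5: 3.76%, or 0.0376 × 112 = 4.2 children per arm.

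Each reclassified child moves an arm's percentage by 1/112 = 0.9 points.

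Not every such child changes class. As an illustration for the look-back reading, assume true change 0, between-child SD 0.4, per-visit SD v = 0.6 to 0.8, and a transfusion rise of 1.5 to 2.5 g/dL at Week 28. The SD of the average is √(0.4² + v²/2) = 0.58 to 0.69. The chance that the average exceeds 1 is 4–7% without transfusion. With it, the mean shifts by 0.75 to 1.25 and the chance becomes 33–67%. The excess is about 0.28 to 0.62, so the expected inflation of one arm's percentage is 0.76% × 0.28 = 0.2 points to 3.76% × 0.62 = 2.3 points. For Week 28 alone, the chance is 8–13% without and 71–98% with transfusion. That case needs both a missing Week 24 value and a recent transfusion, and the documents give no basis for how often the two coincide.

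**The case against.** The strongest reply is that the clause ordinarily means either side. Where the SAP intends one direction it says so: 6.4.2.1, 6.4.2.3 and 6.4.2.4 all speak of the 8 weeks after the transfusion, and 8.2.3 uses different words. On that reading, no transfused value enters the average at target days or anywhere in the protocol visit ranges, provided both draws exist. What is left is conservative: it can remove a responder but cannot create one, and it could be defended as treating transfusion as failure.

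Most of this stands, and it lowers the weight of the point. It does not close it. The direction is still unwritten, no reason is given for counting days after both draws, and a missing Week 24 leaves no anchor.

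One could also argue that the Week 24 Hb assessment means the averaged value. The same sentence speaks against that, because it treats the assessments as separate draws: "Subjects with missing Hb assessment at both Week 24 and Week 28". An average of two draws would also have two dates, not one.

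A reader might infer more: that donor blood inflates Hb response generally, or that the trial's Hb results are biased. The documents do not support this. The inflation needs the less natural reading, a missing Week 24 value, or draws more than 56 days apart. The Hb change analysis has its own clear transfusion rule. The illustration is also unfavourable by design: it sets the drug effect to zero and ignores any fall in Hb that prompted the transfusion. Similar transfusion rates in both arms would cancel much of the effect.

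**Conclusion.** The clause is incomplete on either reading, and the two readings err in opposite directions. At target days each has exactly one error span of 28 days: Days 169–196 missed under look-back, or Days 197–224 wrongly captured under either-side. The lack of an anchor when Week 24 is missing is common to both.

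Severity is minor. Hb response is a percentage by arm with no test stated. It is not among the secondary endpoints in SAP 4.2 or in the testing sequence in SAP 8.2.6, so no tested endpoint is affected. The day counts follow from the SAP's own windows. The numbers of children and percentage points rest on assumed transfusion rates and Hb variability and give only an order of magnitude. The 0.9 to 4.2 children per arm is an upper bound on those rates, because not each transfusion changes a classification.

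**What to change.** Keep the non-responder handling and re-anchor the window. In SAP 8.2.3, replace the transfusion condition with: *or an RBC transfusion in the 8 weeks before any Hb value (Week 24 or Week 28) used for the classification*.

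At target days with both draws present, this covers Days 112–196. Missed days fall from 28 to 0 against the look-back reading, and wrongly captured days fall from 28 to 0 against the either-side reading. If Week 24 is missing, the window becomes Days 140–196, so the anchor problem is solved as well.

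Treating an affected draw as missing and classifying on the other is tempting but is a different endpoint. A child transfused on Days 112–139 is a non-responder under both current readings, yet would then be judged on Week 28 alone.

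SAP 6.3 says the primary study analysis has already been performed. The sponsor should therefore state which reading was programmed, and report in the final analysis how many children are reclassified in each arm. The cost is one clause, a small programming change and a short table note, with no new data.
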